7.4. Assessment of Causality

The relationship or association of the study drug in causing or contributing to the AE will be characterized using the following classification and criteria:

Relationship to Study Drug	Comment
Related	There is reasonable possibility that the event may have been caused by the study drug (e.g., confirmation by positive rechallenge test).
Not Related	The event can be readily explained by the participant's underlying medical condition, concomitant therapy, or other causes, and therefore, the investigator believes no relationship exists between the event and the study drug.

The investigator should assess causality by answering either "related" or "not related" to the question "Is there a reasonable possibility that the event may have been caused by the study drug?"

The following factors may be used in consideration of causality assessment:

- Challenge/rechallenge: Did the event abate after study treatment was reduced or interrupted? Did the event reappear after study treatment was reintroduced?
- Temporal relationship and time to onset plausibility.
- Confounding risk factors.
- Amount and duration of study treatment exposure.
- Concomitant medications.

7.5. Reporting Adverse Events

All AEs and SAEs must be recorded and reported, regardless of cause or relationship, that occur after the participant signs informed consent through the Part1/Part 2 EOS or Safety Follow-up visit, whichever is later. Any unresolved AEs and SAEs will be followed up through satisfactory clinical resolution. Additionally, SAEs considered related to study treatment that occur at any time should be reported by the investigator regardless of the AE/SAE collection window.

Definitions describing what is and is not considered an AE are provided in [Section 7.1](#).

Information to be collected includes the following:

- Event term
- Time and date of onset
- Investigator-specified assessment of severity and relationship to study drug
- Time of resolution of the event

- Seriousness
- Any required treatment or evaluations
- Outcome

The Medical Dictionary for Regulatory Activities (MedDRA) Version 21.1 or later will be used to code all AEs.

7.6. Reporting Serious Adverse Events

In the event of any SAE reported or observed during the study, the investigational site is immediately required to complete the AE eCRF within the EDC system, indicating the AE is serious, and at least within 24 hours of becoming aware of the event or aware of new information relating to the event. In the event that the EDC system is not available, a paper SAE Report Form should be used and emailed to [REDACTED] according to the instructions provided in the Study-Specific Regulatory Binder

The participant's condition will be followed up by the investigator or designated sub-investigator until resolution of the condition, as described in [Section 7.8](#). If additional visits are required, the participant will be asked to return to the investigational site for further follow-up. As additional information becomes available, such as hospital discharge notes and participant medical records, the investigator will be notified and provided with all relevant information.

It is the investigator's responsibility to report all SAEs to Alector (covered in [Section 11.6](#)), and it is Alector's responsibility to ensure that all safety reporting obligations are carried out in compliance with current legislation for expedited reporting of SAEs (including Suspected Unexpected Serious Adverse Reaction (SUSARS)).

7.6.1. Protocol-Specific Disease Progression Adverse Event and Serious Adverse Event Reporting Requirements

Disease progression in this study is measured via the CDR® plus NACC FTLD and other cognitive and functional assessments. Changes in these scores that are consistent with the expected rate of progression of the underlying disease should not be recorded as AEs.

However, symptomatic deterioration or events that are judged by the investigator to be inconsistent with normal disease progression or are considered related to study treatment should be reported as AEs, and if any of the "serious" criteria are met, it must be reported as an SAE.

Please note that the term "disease progression" should not be reported, but rather the clinical manifestation(s) with applicable descriptors should be captured on the Adverse Event eCRF page.

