2. STUDY OBJECTIVES AND ENDPOINTS

The objectives and endpoints of this study are provided in [Table 1](#) and [Table 2](#).

Table 1: Part 1 (Treatment Period): Study Objectives and Endpoints

	Objective(s)	Endpoint(s)
Primary	The primary objective of the treatment period of the study is to evaluate the safety and tolerability of IV administration of AL001 over 96 weeks in asymptomatic and symptomatic carriers of a GRN mutation causative of FTD and in symptomatic carriers of a C9orf72 mutation causative of FTD.	
Primary Safety Endpoints:
 
To assess the potential effect of cumulative exposure on the safety profile of AL001, the following will be evaluated by dose, such as by using tertiles of the actual dose (normalized to weight) received:
 
 • Incidence, nature, and severity of AEs and SAEs • Incidence of treatment discontinuations and study discontinuations due to AEs • Physical examination abnormalities • Neurological examination abnormalities • Changes in vital signs from baseline over time • Changes in ECGs from baseline over time • MRI abnormalities after dosing relative to baseline • Changes in clinical laboratory tests from baseline over time • Sheehan Suicidality Tracking Scale (Sheehan-STS) • Incidence of ADAs to AL001
Secondary	The secondary objectives of the treatment period of the study are to evaluate the effect of IV administration of AL001 over 96 weeks in asymptomatic and symptomatic carriers of a GRN mutation causative of FTD and in symptomatic carriers of a C9orf72 mutation causative of FTD on the following:	
	
Secondary PK Objective:
 
 • PK 	
Secondary PK Endpoints:
 
 • Serum concentration of AL001 at specified time points • AL001 PK parameters (if data permit) 
 ◦ C_{max} ◦ C_{trough} ◦ AUC_{ss}
	
Secondary PD Biomarker Objectives:
 
 • Longitudinal plasma and CSF PGRN concentration levels • Longitudinal levels of Sortilin in WBCs 	
Secondary PD Biomarker Endpoints:
 
 • The overall change from baseline in PGRN in CSF • The overall change from baseline in PGRN in plasma • The overall change from baseline in Sortilin in WBCs plasma

Table 1: Part 1 (Treatment Period): Study Objectives and Endpoints (Continued)

	Objective(s)	Endpoint(s)

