6.5.6. Neurological Examinations

A complete neurologic examination should include the evaluation of consciousness, orientation, cranial nerves, motor and sensory system, coordination and gait, and reflexes. Limited or symptom-directed examinations will be performed at all other specified time points. A symptom-directed neurological examination should focus on the affected organ system or body area.

For visits with study drug administration, this should be completed prior to study drug infusion. Additional examinations may be completed as clinically indicated.

Record abnormalities observed at screening on the General Medical History and Baseline Conditions page of the eCRF. At subsequent visits, record new or worsened clinically significant abnormalities as AEs on the AE eCRF.

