7.1. Definitions of Adverse Events

The investigator is responsible for reporting all AEs that are observed or reported during the study, regardless of their relationship to study drug or their clinical significance.

An AE is defined as any untoward medical occurrence in a participant enrolled into this study regardless of its causal relationship to study drug. Participants will be instructed to contact the investigator at any time after informed consent signature if any symptoms develop. Study participants should be instructed to report all AEs to the investigator. All AEs must be appropriately documented in the participant's original source documents and on the eCRFs. Investigators should report the diagnosis rather than list symptoms, whenever possible.

An AE does not include the following:

- Elective medical or surgical procedures planned prior to the start of study treatment (e.g., hip replacement surgery) that did not result from a worsening of a previous condition. The condition that led to the procedure may be an AE and must be reported.
- Pre-existing diseases, conditions, or laboratory abnormalities present or detected at the screening visit that do not worsen.
- Situations where an untoward medical occurrence has not occurred (e.g., hospitalization for study drug administration per institutional guidelines, elective surgery, social and/or convenience admissions).
- Overdose without clinical sequelae.
- Any medical condition or clinically significant laboratory abnormality that has an onset date before the consent form is signed and that is not related to a protocol-associated procedure is not an AE. It is considered to be a pre-existing medical condition and should be documented on the medical history eCRF. However, deterioration of a medical condition or new or worsened clinically significant abnormality during the study should be reported as an AE.
- Any AE that began during the Phase 1 study (AL001-1) and was ongoing at the time of enrolling in this study (AL001-2) will not be considered an AE, but medical history.

Adverse events resulting from concurrent illnesses, reactions to concurrent illnesses, reactions to concurrent medications, or progression of disease states must also be reported in the established time frames.

A treatment emergent adverse event (TEAE) is defined as any event not present before exposure to study drug, or any event already present that worsens in either intensity or frequency after exposure.

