6.5. Physical and Neurological Examinations

A complete PE includes evaluation of the head, eyes, ears, nose, and throat, and the cardiovascular, dermatological, musculoskeletal, respiratory, and gastrointestinal systems. Breast, genital, and rectal examinations are not required, unless warranted in opinion of the

health care provider. The examination will be performed by a physician, or a nurse practitioner or physician's assistant under the supervision of a physician.

A limited, symptom-directed examination will be performed at all other specified time points, prior to study drug administration (if applicable) or as clinically indicated.

Abnormalities observed at screening will be recorded on the General Medical History and Baseline Conditions page of the eCRF. At subsequent visits, new or worsened clinically significant abnormalities will be recorded on the AE eCRF.

A complete neurologic examination will include the evaluation of consciousness, orientation, cranial nerves, motor and sensory system, coordination and gait, and reflexes. Changes from baseline abnormalities and changes from previous neurological examinations should be recorded at each subsequent neurologic examination. New or worsened abnormalities should be recorded as AEs on the AE eCRF if considered clinically significant.

Physical and neurologic examinations will be collected at the timepoints identified in [Appendix 14.1](#), [Appendix 14.2](#), [Appendix 14.4](#) and [Appendix 14.5](#).

Physical and neurological examinations will not be summarized or listed since exam results are only entered on the General Medical History and Baseline Conditions or AE pages of the eCRF

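### The protocol's AE-recording rules on disease progression conflict, and the SAP drops the examination summaries, so neurological signs judged expected and unrelated can be missing from the primary safety data

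*Protocol*

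**What the plan says.** **What counts as an AE.** Protocol 7.1 says that AEs resulting from "progression of disease states must also be reported in the established time frames". Its list of what is not an AE does not include expected progression. Protocol 7.5 points to 7.1, not to 7.6.1, for the definition.

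**Examination findings.** Protocol 7.3 makes an out-of-range examination finding an AE if it is confirmed and the investigator considers it clinically significant. Protocol 6.5.6 says of neurological examinations: "At subsequent visits, record new or worsened clinically significant abnormalities as AEs on the AE eCRF". Neither has a progression exception.

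**The progression section.** Protocol 7.6.1 makes three statements:
- On clinical outcome assessment (COA) scores: "Changes in these scores that are consistent with the expected rate of progression of the underlying disease should not be recorded as AEs".
- On symptoms, AE reporting is required for "symptomatic deterioration or events that are judged by the investigator to be inconsistent with normal disease progression", or for those considered related to treatment.
- The term disease progression is not to be used; instead "the clinical manifestation(s) with applicable descriptors should be captured on the Adverse Event eCRF page".

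**The analysis.** "Neurological examination abnormalities" is a primary safety endpoint in Table 1 of both documents, as is the incidence, nature and severity of AEs and SAEs. Protocol 8.4.2.5 planned shift tables for the examinations. SAP 6.5 withdraws them: "Physical and neurological examinations will not be summarized or listed since exam results are only entered on the General Medical History and Baseline Conditions". The only other place it names for results is the AE form. SAP 12 repeats this as a change to the planned analysis and names no replacement.

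**The concern.** Take a participant with a new gait or motor sign that the investigator thinks fits the usual course of FTD and is not drug-related. A site working from 6.5.6, 7.1 or 7.3 enters an AE. A site working from 7.6.1 can reasonably leave it off. With the examination tables gone, the AE page is the only place where that sign could reach the analysis.

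Two primary endpoints then depend partly on which section a site follows. A third may too, since a discontinuation for decline counts as due to an AE only if the decline was recorded as one. With a single arm, no between-group comparison would expose the loss.

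**Working it through.** **Step 1. The rules side by side**, for a clinically significant neurological sign judged expected and unrelated:

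| Protocol section | Instruction | Result for this sign |
|---|---|---|
| 7 (opening) | Report if there is doubt | Report, if the investigator has doubt |
| 7.1 | Report AEs from progression of disease | Report |
| 7.3 | Confirmed, clinically significant out-of-range examination findings are AEs | Report |
| 6.5.6 | New or worsened clinically significant abnormality goes on the AE page | Report |
| 7.6.1, symptoms | Report if inconsistent with normal progression or related | Not required, by implication |
| 7.6.1, last paragraph | Record the manifestation rather than the term | Unclear whether expected progression is covered |
| Appendix 3, home infusion | Abnormalities in the substitute assessment are recorded as AEs | Report |

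The same sign can be treated differently by section, and even by whether the visit was at home or on site. No section sets an order of precedence.

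**Step 2. Is there another record?**
- COAs are summarised in the safety population (SAP 2.3.2 and 9). They cover cognition, behaviour and function, but are exploratory and do not record cranial-nerve, motor, sensory or reflex findings or a neurological gait examination.
- Safety MRI is listed (SAP 6.8). It is not a clinical examination.
- SAP 6.5 says that changes should be recorded at each neurological examination, but the same section says the only eCRF pages holding results are history/baseline and AE.
- Source documents exist outside the analysis database.

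The gap is therefore confined to examination signs of the kind in Step 1.

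**Step 3. The plan's detection figures.** Protocol 8.1 and SAP 2.1 give the probability of at least one clinically significant finding among 40 participants, which is 1 − (1 − p)^40:
- p = 0.1%: 3.92% (stated 3.9%)
- p = 1%: 33.10% (stated 33.1%)
- p = 5%: 87.15% (stated 87.1%)
- p = 10%: 98.52% (stated 98.5%)

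All four reproduce. They assume that every such event is recorded. If only a share c of true events is entered, the formula becomes 1 − (1 − c·p)^40. For p = 5% and c = 50%: 1 − 0.975^40 = 63.7%.

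| Assumed c | p = 0.1% | p = 1% | p = 5% | p = 10% |
|---|---|---|---|---|
| 100% | 3.9% | 33.1% | 87.1% | 98.5% |
| 75% | 3.0% | 26.0% | 78.3% | 95.6% |
| 50% | 2.0% | 18.2% | 63.7% | 87.1% |
| 25% | 1.0% | 9.5% | 39.5% | 63.7% |

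The documents give no value for c, so these rows are illustrations and not estimates. The plan's own examples are drug-related events, which 7.6.1 keeps reportable. The lower rows therefore apply only to a drug-caused event that the investigator takes to be expected and unrelated.

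**The case against.** The sponsor can say that the contradiction is partly inferred. The only explicit instruction not to record concerns COA scores. For symptoms, 7.6.1 says what should be reported, and the exclusion is read into its condition. Its last paragraph can be read as agreeing with 7.1, and the opening of Section 7 tells a doubtful site to report. Behavioural worsening is scored every 12 weeks in Part 1 and summarised. All of this stands, and it narrows the point to the signs named above.

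It does not remove the point. The advice on doubt helps only an investigator who has doubt, and 7.6.1 asks for a judgement against an expected rate that the documents never quantify. The duty to report related events is a weak backstop here: Protocol 7.4 defines an unrelated event as one readily explained by the participant's underlying condition, among other causes, so a sign that looks like FTD can fail both tests for the same reason.

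The sponsor can also say that dropping the examination tables is a separate, disclosed change. It is disclosed, but it is what turns an ambiguity about recording into a possible loss of primary safety data.

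A reader might go further and infer that the primary objective cannot be answered for the nervous system. The documents do not support that: related events, and events judged atypical for FTD, are reportable under every section. A reader might also infer that the missing control arm deprives the investigator of a reference when deciding. An investigator in a randomised trial would have no control data at that moment either.

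**Conclusion.** The recording rules conflict and need reconciling, and a listed primary endpoint has been left without an analysis. The possible loss is limited to motor, gait, sensory, cranial-nerve and reflex findings judged both expected and unrelated. This rests on reading the condition on symptoms in 7.6.1 as an exclusion, which is a natural reading but not an explicit one.

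The size of any loss cannot be derived. A reader might be tempted to put a figure on the swing in AE incidence between sites following different sections. The documents give no rate of clinically significant neurological worsening and no share of events that sites would leave off, so such a figure would be invented.

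Complete recording would not by itself show whether AL001 speeds FTD-like decline, because a single-arm study cannot attribute it. What is at stake is whether the primary safety data are complete and consistent across sites.

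**What to change.** - **Protocol 6.5.6, 7.1, 7.3 and 7.6.1:** adopt one rule. New or worsened clinically significant neurological examination findings, and any event meeting a seriousness criterion, go on the AE eCRF with a yes/no field for consistency with expected FTD progression. Changes in COA scores alone stay out.
- **SAP 6.1:** tabulate TEAEs and SAEs twice, with and without flagged events.
- **SAP 6.5:** report the number of participants with any new or worsened neurological abnormality, taken from those records.

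The field relies on the same investigator judgement as 7.6.1 does now, but that judgement would then classify an event instead of deciding whether it is recorded at all.

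The cost is protocol wording, one eCRF field, a repeat of existing AE tables and one participant count. The downside is more AE records and a higher headline AE incidence; the second set of tables shows how much of that comes from flagged events.

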7.7. Assessment of Severity

The severity, or intensity, of an AE refers to the extent to which an AE affects the participant's daily activities. Severity will be graded according to the World Health Organization (WHO)

Toxicity Grading Scale, March 2019 or later. If an AE is not specified within the WHO Toxicity Grading Scale, then the AE will be graded according to the following definitions:

Grade	Severity	Description
1	Mild	Transient or mild discomfort; no limitation in activity; no medical intervention or therapy required. The participant may be aware of the sign or symptom but tolerates it reasonably well.
2	Moderate	Mild to moderate limitation in activity; no or minimal medical intervention/therapy required.
3	Severe	Marked limitation in activity; medical intervention/therapy required; hospitalizations possible.
4	Life-threatening	The participant is at risk of death due to the adverse experience as it occurred. This does not refer to an experience that hypothetically might have caused death if it were more severe.
5	Death	Any AE where the outcome is death.

It should be pointed out that the term “severe” is a measure of intensity and that a severe AE is not necessarily serious.

Changes in the severity of an AE should be documented to allow an assessment of the duration of the event at each level of intensity to be performed. Adverse events characterized as intermittent do not require documentation of onset and duration of each episode. When the intensity of an AE changes more than once a day, the maximum severity for the event should be listed. If the intensity changes over a number of days, these changes should be recorded separately (e.g., as having distinct onset dates).

7.8. Follow-up of Participants Reporting Adverse Events

All AEs must be reported in detail on the appropriate page in the eCRF. The investigator should follow each AE and SAE through satisfactory clinical resolution.

All AEs and SAEs that have not resolved by the end of the study or that have not resolved upon discontinuation of the participant’s participation in the study must be followed up until any of the following occurs:

- The event resolves.
- The event stabilizes.
- The event returns to baseline, if a baseline value is available.
- The event can be attributed to agents other than the study drug or to factors unrelated to study conduct.
- It becomes unlikely that any additional information can be obtained (participant or health care practitioner refusal to provide additional information, lost to follow-up after demonstration of due diligence with follow-up efforts).

After the protocol-defined follow-up period, Alector (or designee) should be notified if the investigator becomes aware of any SAE that is believed to be related to prior study drug.

7.9. Infusion Reactions

Signs or symptoms of AEs during the infusion will be carefully monitored and treated according to institutional guidelines. Further details regarding infusion-related reactions are provided in [Section 5.1.2](#) of this protocol and in the IB.

7.10. Anaphylaxis

Signs or symptoms of anaphylaxis will be carefully monitored and treated according to institutional guidelines. Emergency crash cart equipment and medications, including multiple doses of epinephrine, pressors, and bronchodilators, will be available at all times during the infusion portions of the study.

